### **3.1.4 Definition of Maximum Feasible Dose (Modules 1 and 2)**

A dose and schedule will be considered non-feasible and escalation will cease where PK parameters determine that a maximum absorbable dose has been reached, or where a formulation that would allow administration of RXC004 in a reasonable number of capsules of an acceptable size is not achievable.

### 3.1.5 Definition of MBAD (Modules 1 and 2)

- A biologically relevant PK exposure (i.e. dose predicted to sustain free plasma concentration  $>IC_{50}$ ). The estimated biologically relevant PK exposure is calculated to be achieved by a dose of 0.5 mg QD;

And/or

- Biomarker (AXIN2) target engagement in either normal or tumour tissue;

And/or

- Clinical response (RECIST 1.1).

## 3.2 Safety Review Committee

Following the completion of each dose escalation cohort of Modules 1 and 2, the SRC will meet by telephone to evaluate the safety and tolerability and, where available, PK and pharmacodynamic of RXC004 to decide the next dose and/or schedule. Any dose interruptions and reductions will be taken into account. AEs occurring in Cycle 2 and beyond which meet the definition of a DLT or are considered clinically significant may also be considered in making dose escalation decisions (refer to RXC004 Safety Review Committee Remit, which has been provided as a separate document). Other AEs, or possible trends in AEs, during the dose escalation phase may inform dose escalation decisions.

The SRC will consist of the following:

- Principal Investigator or delegate
- IQVIA Project Manager, who will chair the committee, or delegate
- Redx Chief Medical Officer
- Redx Project Manager
- Investigator or delegate from other investigational sites

The Clinical Pharmacology Scientists, Study Statisticians, Pharmacovigilance representatives, Study Leaders and other Sponsor and non-Sponsor technical experts may also be invited as appropriate. The SRC Remit document for this study will define the exact membership and who should be present for decisions to be made. Further Sponsor or non-Sponsor experts may be consulted by the SRC as necessary.

The SRC decisions may be to:

- Proceed with dose escalation either to next defined dose escalation step or justify the rationale for reduced escalation step based on available safety, PK and pharmacodynamic data
- Expand the cohort to a maximum of 6 evaluable patients

- De-escalate the dose of RXC004 either to a previous lower dose level (up to a maximum of 6 evaluable patients) or to an intermediate lower dose level
- Stop the dose escalation part of a study module
- Adjust the dosing frequency/schedule/sequence of RXC004, with or without a concurrent change in dose
- Advise on any adjustment to study assessment time points e.g. PK sampling, based on data available during the trial and protocolled limit on blood volumes and number of samples permissible in a given period.

Following establishment of the monotherapy dose in Module 1 (MBAD/ MTD/ MFD), the SRC decisions may be to:

- Confirm the MTD, MFD, and/or MBAD
- Advise on (and approve where appropriate) required pre-medication
- Advise on any adjustment to study assessment time points e.g. PK sampling, based on data available during the trial and protocolled limit on blood volumes and number of samples permissible in a given period.

When there are other patients who are ongoing within a cohort at the time of a review, the SRC may decide to defer their decision until data from these further patients become evaluable.

Any patient started on treatment in error, as he/she failed to comply with all of the selection criteria but meets the criteria of an evaluable patient, will be reviewed on a case by case basis by the SRC to determine if the patient should be included or excluded in the decision for dose escalation. The decisions and decision-making of the SRC on the next dose level will be documented and provided to the Investigators prior to dosing any new patients.

### **3.3 Dose Modifications and Individual Stopping Criteria**

The module specific dose modification guidelines and individual stopping criteria in found in Section 5.2 (Module 1) Section 5.3 (Module 2), and Section 5.4 (Module 3) respectively.

### **3.4 Adverse Event Management Plan**

#### **3.4.1 Bone Management plan (All Modules)**

[figure not shown]
##### **Bone Metabolism Overview**

Bone is a metabolically active structure which undergoes continuous remodelling throughout life. {Crockett, 2011 Ref 5} After attaining peak bone mass, bone undergoes constant remodelling through bone resorption followed by formation sequentially by a basic multicellular unit of bone called a “bone remodelling unit”. Various biomolecules, released

into the circulation during bone resorption and formation, are called bone turnover markers (BTMs). Under optimal physiological conditions, bone resorption takes place in around 10 days.

### Figure 3 Bone Remodeling Schematic

Schematic representation of the bone remodelling cycle, increased bone resorption is accompanied by an increases in  $\beta$ -CTX.

The BTMs are grouped into two categories based on the metabolic phase during which they are produced as:

- Bone formation markers
- Bone resorption markers

N-terminal propeptide of type 1 collagen (PINP) is a recognised by the International Osteoporosis Foundation (IOF) as a bone formation marker, in view of its predictable response to treatment and the reliability of PINP assays as evidenced by low intra-individual variability, smaller circadian variation, stability at room temperature, and a good assay precision. C-terminal telopeptides of type 1 collagen (CTX-1) are degradation products of Type 1 collagen of bone generated by the activity of the enzyme cathepsin K. The native CTX exists in two forms,  $\alpha$  and  $\beta$  isomerised forms, with the latter being released from the resorption of mature bone.

Serum  $\beta$ -CTX is a well-characterised, established biochemical marker of bone resorption and is recommended in guidelines and advice from authorities such as the International Federation of Clinical Chemistry and the International Osteoporosis Foundation. {Vasikaran, 2018 Ref 46;Johansson, 2014 Ref 20;Vasikaran, 2011 Ref 44} While it is recognised that increased bone resorption is associated with increased fracture risk, the relationship in prospective studies is a relatively weak one and there is no internationally validated thresholds or criteria that identify a high risk of fracture. A number of studies have recently derived reference intervals for  $\beta$ -CTX and a proposed threshold of 1000 pg/ml is comparable to the upper limit in a number of

these studies. {Vasikaran, 2014 Ref 45;Michelsen, 2013 Ref 27;Gossiel, 2014 Ref 12}  
Currently in this study all patients are required to have a  $\beta$ -CTX level of <1,000 pg/mL to be eligible to receive RXC004. All eligible patients will receive prophylactic denosumab (Anti-RANKL antibody) to minimise bone mineral density loss.

The revised dose escalation range of 0.5–3.0 mg daily is expected to result in exposure levels lower than those observed at tolerated doses of WNT974 and ETC-159 (10 mg and 16 mg respectively; levels at which no fractures were reported).

To further reduce the potential for bone effects Redx will ensure that all patients receive calcium and vitamin D supplementation [vitamin D3 (cholecalciferol)]. In recognition of the fact that increased bone resorption is currently a potentially reversible effect of RXC004 at higher exposures, Redx will introduce treatment with denosumab in patients showing significant increases in  $\beta$ -CTX (increase of  $\geq 350$  pg/mL  $\beta$ -CTX from baseline or to a level above 1,000 pg/mL).

#### **3.4.1.1 Exclusion of Patients at High Risk of Bone Fractures**

The following patients are deemed to be at high risk of bone fractures and will be excluded from the study:

- Patients with bone metastases
- Patients with osteoporosis (as defined by a T-score of < -2.5 at L/R total hip, L/R femoral neck, or lumbar spine (L1-4) by DXA scan) or history of fragility fractures (any fracture occurring with low-level trauma or as a result of falling  $\leq$  standing height)
- Patients with a  $\beta$ -CTX (bone turnover marker) of > 1000 pg/ml
- Patients with Vitamin D [25(OH)D3] deficiency defined as < 30nmol/L (<12ng/mL)
- Patients with history of hyperparathyroidism, Paget's disease or Osteomalacia
- Patients with a corrected total serum calcium level of <2 mmol/L and serum magnesium level of < 0.60 mmol/L
- Patients who have received treatment for type 2 Diabetes Mellitus with a Thiazolidinedione peroxisome proliferator-activated receptor gamma agonist (e.g. pioglitazone or rosiglitazone) within 4 weeks prior to study drug dosing
- Patients who have received oral or intravenous (i.v.) glucocorticoids for  $\geq 4$  weeks at daily doses  $\geq 7.5$  mg of oral (p.o.) prednisolone (or equivalent) within 12 weeks prior to study drug dosing

### **3.4.1.2 Prophylactic Supplements**

The following supplements should be started at screening and continue throughout the RXC004 treatment

- Vitamin D supplements 800 IU daily
- Calcium supplements 1000-1500 mg daily

Vitamin D3 (cholecalciferol) should be used as it is thought to be a more effective supplement.

**Patient who fail screening due solely to 25 (OH)D3 level <12 ng/mL (30 nmol/L)** should be given a single dose of oral cholecalciferol 300,000 IU and the levels rechecked approximately 3 weeks later (and within the 28-day screening window)

Those with values >12 ng/ml can then enter the study if all other entry criteria are fulfilled and will receive the long term prophylactic daily cholecalciferol 800 IU as maintenance throughout the study treatment period.

All patients will receive prophylactic denosumab (120 mg s.c. QM) along with vitamin D3 (cholecalciferol 800 IU QD) and calcium (1000-1500 mg QD) supplements from the time of signing the ICF and throughout the- RXC004 treatment.

### **3.4.1.3 Monitoring of Blood-Bone Turnover Markers and BMD**

#### **BMD**

Osteoporosis and osteopenia are defined based on assessment of BMD using DEXA scan, with osteoporosis defined as a T-score of < 2.5 SD and osteopenia as a T-score of <- 1 and > -2.5 SD. However, BMD has low sensitivity with osteoporotic fractures occurring in both osteoporotic and osteopenic individuals.

BMD will be assessed by DEXA scan at Screening, Cycle 2, and every 3 cycles from Cycle 4 onwards i.e. Cycles 4, 7, 10 etc).

In addition to a baseline (pre-treatment) DEXA scan all patients will have a vertebral fracture assessment (VFA) scan (a lateral T & L spine assessment if a VFA cannot be performed locally) to document any asymptomatic moderate/severe vertebral fractures which occur in a significant minority of patients aged 50 years or older. {O'Neill, 1996 Ref 33} Patients who have an asymptomatic, mild (Grade 1) vertebral fracture but who fulfil all inclusion/exclusion criteria will not be excluded from study. {Johansson, 2014 Ref 20}

#### **Blood-bone turnover biomarkers**

Blood samples for monitoring of the bone turnover markers beta C-terminal telopeptide of type 1 collagen ( $\beta$ -CTX) and P1NP will be routinely collected for patients.

Bone turnover biomarkers will be collected\* at the timepoints detailed in the Schedule of assessments (Appendix 1 for Module 1, Appendix 2 for Module 2 and Appendix 9 for Module 3)

\*note that due to circadian variations and effects of food intake on CTX measurements,  $\beta$ -CTX samples will be collected in the morning after an overnight fast.

The major benefit of using biochemical markers is that treatment induced changes occur much earlier than DEXA measured BMD, and the magnitude of the changes are usually much greater (i.e. a greater signal to noise ratio) than those detected by BMD. Therefore, serum  $\beta$ -CTX levels will be routinely monitored as a resorption marker. Samples will also be stored for subsequent measurement of other bone markers (e.g. P1NP) if indicated, during or at the end of the study.

#### **3.4.1.4 Intervention Measures for Patients with Increased Bone-Fracture Risk on RXC004 Treatment**

The interventions detailed in Table 2 should be followed for all patients on RXC004 study treatment, in the event of increased bone fracture risk.

Patients with a DEXA scan showing  $\geq 7\%$  worsening in BMD at lumbar spine or total hip compared to baseline will permanently discontinue study treatment. The change in BMD that can be confidently detected is termed the least significant change (LSC). A 7% decrease in BMD is approximately the 99% confidence limit for LSC and is considered as an indicator of failure to respond to treatment. {Diez-Perez, 2012 Ref 7}.

Prophylactic denosumab (XGEVATM - 120 mg s.c. QM per approved label for prevention of skeletal-related events (SREs) in patients with bone metastases) will be administered to all patients (from the 1.5mg RXC004 monotherapy Module 1, Cohort 3). This denosumab dose and schedule is being adopted to maximise bone safety. Patients with advanced/metastatic malignancies are at potential increased risk of bone fragility if treated with a porcupine inhibitor such as RXC004. In addition, while patients with bone metastases are excluded from the protocol currently it is the intention (based on safety data and appropriate expert and regulatory review and approval) to administer RXC004 to patients with bone metastases as part of the RXC004 development programme as a significant minority of patients with metastatic disease will have bone metastases). The XGEVATM approved dose and schedule of denosumab will be used in all patients both to maximize bone safety and allow a uniform and accurate assessment of denosumab use in combination with RXC004. Denosumab, as it is a more potent inhibitor of bone resorption compared to bisphosphonates, leads to greater increases in bone mineral density. {Miller, 2016 Ref 28}

Prophylactic use of denosumab was not adopted from start of study treatment as the significantly lower starting dose of RXC004 0.5mg (previously this was 10 mg) and the other bone protection measures reduced the potential for bone toxicity. However, as a significant number of patients (3 of 6) required denosumab treatment by the end of Cycle 1 based on reaching protocol-defined increases in  $\beta$ -CTX levels indicative of increasing risk of bone fragility, prophylactic denosumab is now administered to all patients (from the 1.5 mg RXC004 monotherapy cohort) based on a review of the data and advice by an independent expert in bone metabolism.

**Table 2 Interventions for patients with increasing bone fracture risk**

Event	Intervention
Confirmed RXC004 related fragility bone fracture	
 
Permanently discontinue study treatment
 

Patients with a DEXA scan showing $\geq 7\%$ worsening in BMD at lumbar spine or total hip compared to baseline	
 
Permanently discontinue study treatment
 

An individual increase in $\beta$ -CTX of $\geq 350$ pg/mL from baseline (screening) and/or an individual measurement $\geq 1000$ pg/mL $\beta$ -CTX	
 
If serum <math>\beta</math>-CTX <math>> 1,000</math> pg/mL or <math>\geq 350</math> pg/mL higher than the baseline level - permanently discontinue study treatment unless the patient has received clinical benefit (Investigator assessment) and continued treatment is warranted.
 

### 3.4.2 Diarrhoea/Colitis Management and Treatment Guidelines

Please refer to Appendix 5, for the treatment of diarrhoea/colitis for patients enrolled in all Modules

### 3.4.3 Nivolumab Toxicity Management and Dose Modification (for Module 2 patients)

Guidelines for the management of immune-mediated reactions and infusion-related reactions, for patients treated with nivolumab therapy (Module 2 – RXC004 + nivolumab combination) are provided in the Nivolumab Toxicity Management and Dose Modification guidelines (Appendix 8)

### **3.5 Treatment Compliance and Accountability**

Study drug administration must be performed by study site staff and documented in source documents and the CRF.

The prescribed dosage, timing, and mode of administration may not be changed. Any departures from the intended regimen must be recorded in the eCRFs.

At each visit, prior to dispensing study medication, previously dispensed study medication will be retrieved by the Investigator and compliance assessed. Subjects exhibiting poor compliance as assessed by capsule counts should be counseled on the importance of good compliance to the study dosing regimen.

Noncompliance is defined as taking less than 80% or more than 120% of RXC004 study medication during any evaluation period (visit to visit) or less than 100% of nivolumab at each infusion.

#### **3.5.1 Treatment Accountability**

The Investigator, a member of the investigational staff, or a hospital pharmacist must maintain an adequate record of the receipt and distribution of all study medication using the Drug Accountability Form. These forms must be available for inspection at any time.

All study medication supplies should be accounted for at the termination of the study and a written explanation provided for discrepancies. All unused study medication supplies and packaging materials are to be inventoried and returned to IQVIA by the Investigator. The Investigator is not permitted to return or destroy unused clinical drug supplies or packaging materials unless authorized by IQVIA.

### **3.6 Subject Withdrawal**

Patients may withdraw from any aspects of the voluntary exploratory research at any time, without prejudice to further treatment and independent of any decision concerning participation in other aspects of the main study. Patients may be discontinued from investigational product in the following situations:

- Patient decision. The patient is at any time free to withdraw his/her participation in the study, without prejudice
- Adverse events requiring permanent discontinuation as detailed in Table 4
- Severe non-compliance to this protocol as judged by the Investigator and/or Sponsor
- Confirmed disease progression
- Patients incorrectly initiated on investigational product

- Life threatening or other unacceptable toxicity
- The discovery of an unexpected, significant, or unacceptable risk to the patients enrolled in the study
- Lack of evaluable and/or complete data
- Decision to modify the development plan of the drug
- A decision on the part of the Sponsor to suspend or discontinue development of the drug
- Extraordinary medical circumstances: Subject who, in the opinion of the Investigator should be discontinued for their well-being or if at any time the treatments prescribed by this protocol are detrimental to the subject's health, the subject may be withdrawn from the study. In this event, reasons for withdrawal should be clearly documented on the case report form (CRF).
- If subject becomes pregnant during the treatment period

Any patient who permanently discontinues investigational product should be followed up for at least 28 days and until disease progression.

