### **5.2.7 RXC004 Monotherapy: Dose Modifications**

If a patient experiences a clinically significant and/or unacceptable event including a DLT not attributable to the disease or disease-related processes under investigation, RXC004 dosing may be interrupted or the dose reduced and supportive therapy administered as required.

If the event resolves or reverts to  $\leq$  CTCAE grade 2, treatment with RXC004 may be restarted using the rules below for dose modifications, only following agreement with the Sponsor Physician. Patients who are at the lowest possible dose, i.e., in Cohort 1 or who have their dose previously reduced to the Cohort 1 dose and who have demonstrated an acceptable response to the dose interruption may be permitted to restart at the lowest dose level at the discretion of the Investigator.

For all other events, if the event does not resolve to  $\leq$  CTCAE grade 2 or the patient is not showing clinical benefit, then the patient should be discontinued from treatment and observed until resolution of the event.

Maximum tolerated dose will be defined in the presence of optimal supportive care for the event in question.

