**Table 4 Module 1 Dose Interruption and Stopping Criteria**

Event	Action
Diarrhoea	Treat as per Diarrhoea/Colitis Management and Treatment Guidelines
1st incidence of diarrhoea $\geq$ grade 2 (suspected RXC004 related):	Please refer to Appendix 5 Temporarily interrupt RXC004 for up to 14 days*. Consider restarting at lower dose if resolved to $<$ grade 1
2nd occurrence of $\geq$ grade 2 diarrhoea	Temporarily interrupt RXC004 for up to 14 days*. Consider restarting at lower dose if resolved to $<$ grade 1
3rd occurrence of $\geq$ grade 2 diarrhoea	Permanently discontinue study treatment
Bone events	
Confirmed RXC004 related fragility bone fracture (excluding grade 1 vertebral deformities)	Permanently discontinue study treatment
Patients with a DXA scan showing $\geq$ 7% worsening in BMD at lumbar spine or total hip compared to baseline	Permanently discontinue study treatment
An individual increase in $\beta$ -CTX of $\geq$ 350pg/ml from the baseline (screening) value or in individual measurement of $\geq$ 1000pg/ml	Permanently discontinue study treatment unless the patient has received clinical benefit (investigator assessment) and continued treatment is warranted.
Hepatic events	
Grade 3 increases in ALT or AST or ALP ( $>$ 5 x ULN if baseline normal, $>$ 5 x baseline, if baseline abnormal)	Permanently discontinue study treatment
Grade 2 increases in ALT or AST or ALP ( $>$ 3 x ULN if baseline normal, $>$ 3 x baseline, if baseline abnormal) with the appearance of symptoms associated with a clinical diagnosis of hepatitis including right upper quadrant pain or tenderness, fever, rash or eosinophilia ( $>$ 5%)	Permanently discontinue study treatment

Event	Action
Grade 2 increases in ALT or AST (> 3 x ULN if baseline normal, >3 x baseline, if baseline abnormal) and total bilirubin > 2 x ULN or INR* > 1.5 or other evidence of impairment to the synthesis function of the liver]	Permanently discontinue study treatment
*Unless patient is receiving warfarin	
Other adverse events	
Grade 3-4 toxicity (1 st event ^ )	Interrupt RXC004 (max. 14 days*), resume at the next lowest dose level when resolved (grade ≤ 2 or returns to baseline).
Grade 3-4 toxicity (subsequent events ^ )	Permanently discontinue study treatment

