### **5.3.6 Dose-Limiting Toxicity for RXC004 + Nivolumab Combination (Module 2)**

The DLT assessment period runs from the start of dosing with RXC004 and nivolumab (Cycle 1 Day 1) up to Cycle 1 Day 28 where nivolumab treatment is administered every 28 days starting on C1D1.

A DLT is defined as an AE or abnormal laboratory value that occurs from cycle 1 day 1 up to Cycle 1 Day 28, assessed as unrelated to disease progression, intercurrent illness, or concomitant medications and is possibly related to RXC004, nivolumab or both agents and that despite optimal therapeutic intervention meets any of the following criteria;

1. Haematological toxicity that is:
  - $\geq$  CTCAE grade 4 neutropenia present for more than 4 consecutive days
  - Grade 3 neutropenia ( $ANC \geq 500$  to  $< 1000$  cells/mm^3) of any duration accompanied by fever  $\geq 38.5^{\circ}C$  and/or systemic infection
  - Grade 3 thrombocytopenia ( $25,000$  to  $< 50,000/mm^3$ ) with clinical evidence of bleeding
2. Any other confirmed haematological toxicity  $\geq$  CTCAEv4 grade 4 (a repeat may be required for confirmation of an isolated abnormality in the absence of clinical signs, symptoms or other abnormal investigations, i.e. a suspected spurious value)
3. Non-haematological toxicity  $\geq$  CTCAE grade 3 including:

- Laboratory abnormalities that are considered clinically significant by the investigator (with or without clinical symptoms or signs)
  - QTc prolongation (> 500 msec or 60 msec above baseline)
4. Any other toxicity that:
    - Is greater than that at baseline, is clinically significant and/or unacceptable, and is judged to be a DLT by the SRC
    - Is a protocol defined stopping criteria and is suspected to be RXC004 or Nivolumab related
  5. Any grade 3 or higher immune-related adverse events

A DLT excludes:

1. Inadequately treated grade  $\leq 3$  nausea and/or vomiting and grade  $\leq 3$  diarrhoea
2. Any toxicity clearly unrelated to RXC004 and/or Nivolumab e.g. solely related to the disease or disease-related process under investigation.
3. Isolated laboratory changes of any grade without clinical sequelae or clinical significance

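### Module 1's three mandatory liver stops for RXC004 are missing from the Module 2 and 3 tables, so a Grade 2 rise with bilirubin, INR or hepatitis symptoms is left to judgement

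*Protocol*

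**What the plan says.** Section 3.6 is a core section, so it covers every module. Its list of reasons for which a patient may be discontinued includes "Adverse events requiring permanent discontinuation as detailed in Table 4" and, separately, "Life threatening or other unacceptable toxicity". It does not mention Tables 6 or 7. Section 3.3 treats the criteria as module-specific: "The module specific dose modification guidelines and individual stopping criteria in found in Section 5.2 (Module 1) Section 5.3 (Module 2", continuing to Section 5.4 for Module 3. Sections 5.3.8 and 5.4.7 then name Table 6 and Table 7.

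Table 4 (Module 1) has a hepatic block of three rows, each ending in permanent discontinuation at first occurrence:

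- "Grade 3 increases in ALT or AST or ALP" (above 5x ULN, or above 5x baseline if baseline is abnormal);
- a Grade 2 rise in ALT, AST or ALP "with the appearance of symptoms associated with a clinical diagnosis of hepatitis";
- a Grade 2 rise in ALT or AST with "total bilirubin > 2 x ULN or INR* > 1.5 or other evidence of impairment to the synthesis function of the liver".

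Tables 6 and 7 keep Table 4's bone, surgery, vomiting and missed-dose rows and add colitis, dysgeusia and COVID-19 rows. Neither has a hepatic row for RXC004. Module 2's DLT definition (section 5.3.6, criterion 4) includes any toxicity that "Is a protocol defined stopping criteria and is suspected to be RXC004 or Nivolumab related"; section 5.2.6 has the equivalent clause for Module 1.

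**The concern.** The drug is the same, and Module 3 uses the same 2 mg daily dose already given in Module 1, yet the mandatory liver stops disappear with no visible reason. The combined pattern, a transaminase rise with raised bilirubin or INR, suggests impaired liver function and not just enzyme leakage. Section 2.1.1 requires normal total bilirubin at entry, so a value above 2x ULN is a new change on study. Biliary tract cancer is an eligible tumour for Module 3 (section 2.1.3), so some rises will have a competing tumour cause. That makes a written rule more useful.

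Two things are at stake. One is whether sites act alike on the same liver finding. The other applies to Module 2: the DLT definition refers to stopping criteria, so removing a stopping row also removes an automatic DLT from a 3+3 escalation.

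**Working it through.** The plan states no figure on this point, so the check is a side-by-side reading of the three tables and the rules around them.

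**Step 1: action on RXC004**

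| Liver event | Module 1, Table 4 | Module 2, Table 6 | Module 3, Table 7 |
|---|---|---|---|
| First Grade 3 ALT/AST/ALP rise | Permanent stop | If RXC004-related: interrupt, resume one level lower | If RXC004-related: interrupt, resume one level lower |
| Grade 2 rise with hepatitis symptoms | Permanent stop | Investigator opinion | Investigator opinion |
| Grade 2 ALT/AST with bilirubin >2x ULN, INR >1.5 or impaired synthesis | Permanent stop | Investigator opinion | Investigator opinion |

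Mandatory hepatic stop rows: 3, 0 and 0. Stopping tables cited in section 3.6: 1 of 3. With a normal baseline, the affected Grade 2 band is above 3x and up to 5x ULN. Table 4's hepatic rows do not require attribution to RXC004; the Grade 3-4 rows in Tables 6 and 7 do.

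**Step 2: do the general rules fill the gap in Module 3?** Section 5.4.6 says to discontinue if the event does not resolve to Grade 2 or lower, or if the patient is not showing clinical benefit. A Grade 2 event already meets the resolution threshold, so that limb cannot apply. The benefit limb can. What remains is the patient thought to be benefiting, for whom Table 4 would still have required a stop. Module 1 has a similar organ-neutral sentence in section 5.2.7 ("For all other events, if the event does not resolve to" Grade 2 or lower, or there is no benefit) and has the hepatic rows as well.

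**Step 3: and in Module 2?** Section 5.3.7 permits RXC004 to be held for a clinically significant event of any grade until baseline or Grade 1; a related event unresolved after 14 days must be discussed with the sponsor before restart. Appendix 8 requires a work-up and a nivolumab hold for Grade 2 ALT/AST hepatitis, but sets no RXC004 action. Table 6 lets RXC004 continue while nivolumab is held or stopped if the investigator sees benefit.

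**Step 4: DLT status.** In Module 1, a suspected-related Grade 2 combined or symptomatic rise meets a Table 4 stop and so is a DLT under section 5.2.6. In Module 2, Table 6 has no such row, and the Grade 3 criteria do not reach a Grade 2 event. It becomes a DLT only if the SRC decides so, unless Table 4 is brought in through section 3.6.

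**Step 5: what one classification can change.** Under section 3.1.2, counting one such event moves a cohort from 0/3 to 1/3 (escalate becomes expand to 6), or from 1/6 to 2/6 (tolerated becomes not tolerated). SAP Table 2 lists 2 mg as not applicable under actual dose, so this concerns the 1 mg and 1.5 mg levels.

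**The case against.** The best defence is that Tables 6 and 7 are a deliberate revision. Diarrhoea rows became colitis rows, the recurrence rule was narrowed to the same event, and the corticosteroid row went. Section 5.4.3 reports no Grade 4 or 5 related events up to 2 mg and no liver event among the commonest. Parts of the section 1.7 risk text are not available to us. This stands as a possibility, but nothing visible says that the hepatic rows were removed on purpose.

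A second defence is that decisions are not the investigator's alone. Section 7.2.2 has the medical monitor and the sponsor's chief medical officer review laboratory results, and section 5.4.6 requires the sponsor physician's agreement before a Module 3 restart. Module 2 adds the 14-day discussion and Appendix 8. These safeguards are real and reduce the weight of the point. They govern review, restart or long interruptions; none requires RXC004 to stop.

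A third is that section 3.6 is permissive and sections 3.3, 5.3.8 and 5.4.7 lead to the right tables. That is correct. The reference in 3.6 is incomplete; the substantive gap lies in Tables 6 and 7.

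A reader might go further and infer that Module 3 patients are dosed through a liver event with only three-weekly chemistry. The documents do not support that as a loss from Module 1, which also schedules chemistry on Day 1 only from Cycle 2; unscheduled tests are allowed in both. A reader might also infer that discontinuation counts are distorted between modules. The study is non-comparative, modules are summarised separately, and no such comparison is planned.

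**Conclusion.** The point holds as a cheap improvement. Three mandatory RXC004 liver stops in Module 1 become none in Modules 2 and 3, and the core withdrawal section cites one of the three governing tables. The consequence that matters is limited to the Grade 2 combined or symptomatic rise, which has no mandatory RXC004 stop in either later module and is no longer an automatic DLT in Module 2. The first Grade 3 rule is relaxed, not lost.

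It would be wrong to conclude that liver events in Modules 2 and 3 are uncontrolled, or that the omission is shown to be a mistake.

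The conclusion assumes that the bilirubin rise itself is below Grade 3, since otherwise the Grade 3 rules apply. It also assumes that the event is not set aside as an isolated laboratory change without clinical significance, an exclusion in both DLT definitions. The documents give no rate for these events, so neither the number of patients affected nor the chance of a changed dose decision can be estimated.

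**What to change.** - In section 3.6, cite Tables 4, 6 and 7 by module.
- Add Table 4's two Grade 2 hepatic permanent-stop rows to Tables 6 and 7. If the sponsor's physicians want it, except documented tumour-related biliary obstruction.
- In those rows, call for an INR when ALT or AST exceeds 3x ULN; Table 8 lists bilirubin but not INR.
- Name Table 6 in section 5.3.6, criterion 4.
- Leave the first-event Grade 3 rule to the sponsor's physicians: restore the stop, or confirm interrupt-and-reduce.
- If the rows were removed on purpose, say so and give the reason.

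The cost is a protocol clarification and an occasional extra INR. The downside is possibly a few more mandated stops, including some caused by biliary disease if no exception is written. No extra patients or SAP outputs are needed; the planned eDISH plot and shift tables already display the values.
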